### For Patients with Measurable Disease (i.e., Target Disease)

Target Lesions	Non-Target Lesions	New Lesions	Overall Response	Best Overall Response when Confirmation is Required*
CR	CR	No	CR	$\geq 4$ wks. Confirmation**
CR	Non-CR/Non-PD	No	PR	$\geq 4$ wks. Confirmation**
CR	Not evaluated	No	PR	
PR	Non-CR/Non-PD/not evaluated	No	PR	Documented at least once $\geq 4$ wks. from baseline**
SD	Non-CR/Non-PD/not evaluated	No	SD	
PD	Any	Yes or No	PD	no prior SD, PR or CR
Any	PD***	Yes or No	PD	
Any	Any	Yes	PD	

\* See RECIST 1.1 manuscript for further details on what is evidence of a new lesion.  
\*\* Only for non-randomized trials with response as primary endpoint.  
\*\*\* In exceptional circumstances, unequivocal progression in non-target lesions may be

accepted as disease progression.

Note: Patients with a global deterioration of health status requiring discontinuation of treatment without objective evidence of disease progression at that time should be reported as “*symptomatic deterioration*.” Every effort should be made to document the objective progression even after discontinuation of treatment.

### For Patients with Non-Measurable Disease (i.e., Non-Target Disease)

Non-Target Lesions	New Lesions	Overall Response
CR	No	CR
Non-CR/non-PD	No	Non-CR/non-PD*
Not all evaluated	No	not evaluated
Unequivocal PD	Yes or No	PD
Any	Yes	PD

\* ‘Non-CR/non-PD’ is preferred over ‘stable disease’ for non-target disease since SD is increasingly used as an endpoint for assessment of efficacy in some trials so to assign this category when no lesions can be measured is not advised

#### Duration of Response

Duration of overall response: The duration of overall response is measured from the time measurement criteria are met for CR or PR (whichever is first recorded) until the first date that recurrent or progressive disease is objectively documented (taking as reference for progressive disease the smallest measurements recorded since the treatment started). The duration of overall CR is measured from the time measurement criteria are first met for CR until the first date that progressive disease is objectively documented.

Duration of stable disease: Stable disease is measured from the start of the treatment until the criteria for progression are met, taking as reference the smallest measurements recorded since the treatment started, including the baseline measurements.

#### **Progression-Free Survival**

Progression-Free Survival (PFS) is defined as the duration of time from start of treatment to time of recurrence, progression, or death, whichever occurs first.

#### **Survival**

Survival is defined as the duration of time from start of treatment to time of death or the date of last contact

### **13.1 CRITERIA FOR REMOVAL FROM STUDY**

Patients may withdraw from the study at any time. Any patient who withdraws will be encouraged to return to the study center for a treatment completion visit. Patients who

discontinue early should return within 30 days following the final dose of study treatment. The primary reason for discontinuation must be recorded in the medical record.

Patients may be withdrawn from the study if they experience any of the following:

- Disease progression, per investigator assessment
- Intolerable toxicity of LY3023414

Other reasons for patient discontinuation may include, but are not limited to, the following:

- Change in patient eligibility
- Non-compliance
- Patient decision
- If the patient becomes pregnant
- If patient requires more than 2 dose reductions of LY3023414
- If treatment is delayed for more than 28 consecutive days

The investigator has the right to discontinue a patient from the study for any medical condition that the investigator determines may jeopardize the patient's safety if he or she continues in the study; for reasons of noncompliance (e.g., missed doses, visits); or if the investigator determines it is in the best interest of the patient.

#### **14.1 BIOSTATISTICS**

This study aims to assess the activity of LY3023414 in patients with PI3K-pathway activated recurrent or persistent endometrial cancer as measured by the best overall response rate as determined by RECIST 1.1. Assuming we use a binary endpoint of response, defined as best overall response of CR or PR versus not, a sample size of 25 patients provides 90% power to test the hypothesis that the response rate is promising (defined as 30% or higher) against a non-promising rate of 10% or lower. This calculation is based on historical data from studies with ineffective agents in a similar patient population, which have ORR < 10% and PFS rate at 6 months < 20% (Fracasso et al, 2006, Schilder et al. 2004, Garcia et al. 2008 Aghajanian et al, 2011), and uses an exact, one-sample test for binomial proportion, with Type I error=10%. At the end of the study, if at least 5/25 responses are observed then this will be considered a positive study (i.e. conclude that RR is >10%).

Based on historical accrual rates in similar populations, and with the increased prior lines of therapy that will not be allowed for eligibility, we anticipate successful enrollment of 2 patients per month yielding a total accrual time of 12 months. Accrual will continue until 25 evaluable for response patients are treated (evaluable patients are defined in section 12.1)

In addition we will report the following statistics:

1. The clinical benefit rate (CBR) of LY3023414 therapy, defined as the percentage of patients with complete response (CR) + partial response (PR) + stable disease (SD)  $\geq 12$

- weeks from the start of treatment will be reported and the 90% confidence interval will be estimated using exact binomial proportions
2. Progression free survival (PFS), defined as the duration of time from start of treatment to time of recurrence, progression, or death due to any cause, whichever occurs first. Patients will be censored at last follow up date. The Kaplan Meier estimate of median PFS will be reported.
  3. Overall survival (OS), defined as the duration of time from start of treatment until the date of death due to any cause. Patients will be censored at last follow up date. The Kaplan Meier estimate of median OS will be reported.
  4. The duration of response (DOR) of LY3023414 therapy, defined as the time from which measurement criteria are met for CR or PR (whichever status is recorded first) until the first date of documented disease progression, will be estimated using the Kaplan Meier method. Patients without documented progression will be censored at last follow up.
  5. Adverse events by the current version of Common Terminology Criteria for Adverse Events version 4 (CTCAE v4.0) will be tabulated in order to assess the safety profile and tolerability of LY3023414 therapy in patients with PI3K activated recurrent/persistent endometrial cancer.

In addition the study will analyze the following variables as part of assessing exploratory aims in a subset of patients who consent to 12-245:

1. For patients who have not already had their tumors molecularly profiled using the MSK-IMPACT platform, pretreatment archival tumor tissue will be obtained for this purpose. Genomic alterations defined by MSK-IMPACT testing performed on this pretreatment archival tumor tissue will be correlated to objective responses outcomes in an exploratory manner. Consent for this testing, to be performed in the CLIA laboratory, will be obtained through a companion study MSKCC IRB# 12-245. Genomic alterations will be binary and Fisher's exact test will be used to assess the correlation between genomic alterations and response (binary).
2. Serial pre-, on- and post-treatment blood samples will be collected for cell-free tumor DNA analysis and sequenced using continuous quantitative methods (digital droplet PCR or hybridization capture next-generation sequencing) for the PI3K- pathway alterations identified by pre-treatment archival tumor testing and descriptively correlated to clinical outcome. Pre and post treatment samples will be assessed graphically and pre treatment archival tumor testing will be assessed graphically with clinical outcome.
3. Patients who respond to therapy and then progress will be offered optional consent to MSKCC IRB# 12-245 Part B in order to obtain post-progression material for molecular profiling in order to determine the mechanism(s) underlying acquired resistance. A subset analysis of patients who progress and have post progression material for molecular profiling will be performed in order to determine the mechanism(s) underlying acquired resistance. Specifically, we will be looking for presence of genetic alterations which based on their understood biological mechanism may explain acquired resistance (for example, second "hits" on the PI3K pathway).

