## **2.2 SECONDARY OBJECTIVES**

The secondary objectives of this study are as follows:

1. To determine the clinical benefit rate (CBR) of LY3023414 therapy, defined as the percentage of patients with complete response (CR) + partial response (PR) + stable disease (SD)  $\geq 12$  weeks from the start of treatment.
2. To determine progression free survival (PFS), defined as the duration of time from start of treatment to time of recurrence, progression, or death due to any cause, whichever occurs first.
3. To determine overall survival (OS), defined as the duration of time from start of treatment until the date of death due to any cause.
4. To determine the duration of response (DOR) of LY3023414 therapy, defined as the time from which measurement criteria are met for CR or PR (whichever status is recorded first) until the first date of documented disease progression.
5. To assess the safety profile and tolerability of LY3023414 therapy in patients with PI3K activated recurrent/persistent endometrial cancer.

[figure not shown]

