## 10.0 EVALUATION DURING TREATMENT/INTERVENTION

PARAMETER	Screening		Cycle 1			Cycle 2+	End of Treatment	Follow-up
Day	28 days before start	7 Days before start	1	8 ±3 days	15 ±3 days	1 ±4 days	30 days ±14 days	Every 3 months until death ±1 month
Medical History	X							
Physician Examination	X		X	X	X	X	X	
Performance Status	X		X	X	X	X	X	
Height	X							
Weight		X	X	X	X	X	X	
Vital Signs (blood pressure, heart rate and temperature)	X		X	X	X	X	X	
Adverse Event Assessment			X	X	X	X	X	
CBC, differential, hemoglobin, platelets, Electrolytes, BUN, Creatinine, Ca, Mg, Phosphorus, Bilirubin, AST/SGOT, ALT/SGPT, Alkaline Phosphatase		X	X 	X	X	X	X	
Fasting (≥8 hours) Blood Glucose		X	X 	X	X	X	X	
Insulin Level		X	X 	X	X	X	X	
Hemoglobin A1c		X	X 			X	X	

PARAMETER	Screening		Cycle 1			Cycle 2+	End of Treatment	Follow-up
Day	28 days before start	7 Days before start	1	8 ±3 days	15 ±3 days	1 ±4 days	30 days ±14 days	Every 3 months until death ±1 month
PT, INR, PTT		X					X	
Pregnancy test		X 					X	
CA125		X	X 			X	X	
Electrocardiogram	X			X		X	X	
CELL-Free DNA			X	X		X (Odd cycles Day 1 only)		
Radiographic disease assessment	X					X 	X 	X 
Patient drug diary					X			
Survival Follow-up								X 

1. If the patient is of child-bearing potential per MSKCC guidelines. Must be obtained within 72 hours prior to initiating protocoltherapy.
2. Study can be omitted on Cycle 1 Day 1 with screen labs performed within 72 hours.
3. Performed during week 3 of each even numbered cycle (Days 15-21).
4. Only if patient discontinues for reasons other than progression, repeated every 3 months +/- 2 weeks until disease progression or initiation of alternative anti-cancer therapy.
5. Phone call every 3 months.

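### PFS and DOR are censored at last follow-up, the rule used for OS, and DOR also censors deaths, so both medians can be overstated

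*Combined protocol and SAP*

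**What the plan says.** Section 14.1, item 2, defines PFS as time to recurrence, progression or death from any cause and then states: "Patients will be censored at last follow up date. The Kaplan Meier estimate of median PFS will be reported". Item 3 gives OS the same rule: "Patients will be censored at last follow up date. The Kaplan Meier estimate of median OS will be reported". Item 4, on DOR, reads: "Patients without documented progression will be censored at last follow up".

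No section defines last follow-up. The nearest text is the survival definition in section 12, which runs to "time of death or the date of last contact".

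The section 10.0 calendar has two kinds of follow-up after treatment. Footnote 4 continues scans every 3 months for patients who stop for a reason other than progression, but only "until disease progression or initiation of alternative anti-cancer therapy". Footnote 5 covers survival: "Phone call every 3 months", and the column heading runs this until death.

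DOR omits death in all three places where it is defined. Section 2.2, item 4, and section 14.1, item 4, end it at documented progression. The Duration of Response text in section 12 runs "until the first date that recurrent or progressive disease is objectively documented".

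**The concern.** A date of last contact suits OS, because a phone call establishes whether the patient is alive. It does not suit an endpoint that needs imaging. Once scans stop, progression cannot be documented, yet the patient stays in the risk set until the last call or death. Unscanned time, including time on the next therapy, is then credited to LY3023414.

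The exposed group is foreseeable. Sections 11.1 and 13.1 give several routes off drug without progression (related toxicity, repeated dose reductions, non-compliance, patient decision), and footnote 4 plans for such patients.

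For DOR, censoring a death treats the response as if it might have continued. With few responders (5 is enough for a positive study), one or two such deaths can move the median. Both endpoints are secondary and descriptive. However, section 14.1 characterises ineffective agents partly by a 6-month PFS below 20%, so readers are likely to compare this trial's PFS with that figure.

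**Working it through.** **The plan's own figure.** Section 14.1 gives no planning value for PFS or DOR. Its one design claim reproduces: with n = 25 and success at 5 or more responses, exact binomial power at 30% is 0.9095 and type I error at 10% is 0.0980. Censoring dates do not enter that test.

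**PFS, mechanism.** The Kaplan–Meier estimate is S(t) = ∏(1 − dᵢ/nᵢ). An unscanned patient stays in nᵢ but cannot add a progression to dᵢ, so each factor is too close to 1 and the median moves later.

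**PFS, simulation.** Everything here is assumed except n = 25 and the 6-week scan interval (2 cycles of 21 days, section 4.1): true median 2.5 or 4 months, median post-progression survival 6 or 8 months, administrative follow-up 12–24 months, 3,000 trials per scenario. Under the planned rule, a patient who switches has an event at death or is censored at the last 3-monthly call. Selected mean medians in months:

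| Switching | True median | Liable to switch | Complete scanning | Planned rule | Last-scan censoring | Switch as event |
|---|---|---|---|---|---|---|
| Unrelated to prognosis, at 0.7–4 months | 2.5 | 0% | 3.25 | 3.25 | 3.25 | 3.25 |
| | 2.5 | 10% | 3.21 | 3.34 | 3.21 | 2.97 |
| | 2.5 | 20% | 3.23 | 3.50 | 3.22 | 2.77 |
| | 2.5 | 30% | 3.24 | 3.71 | 3.23 | 2.59 |
| | 4 | 10% | 4.77 | 5.07 | 4.77 | 4.22 |
| | 4 | 20% | 4.76 | 5.48 | 4.79 | 3.72 |
| | 4 | 30% | 4.77 | 5.89 | 4.83 | 3.30 |
| At 60–100% of time to progression | 2.5 | 20% | 3.23 | 3.97 | 3.68 | 3.00 |
| | 4 | 20% | 4.79 | 5.93 | 5.59 | 4.49 |

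The bias is the planned-rule value minus the complete-scanning value, for example 5.07 − 4.77 = 0.30. Across all scenarios with unrelated switching:

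- 5–10% liable (about 1–2 patients): overstated by 0.06–0.30 months, with the reported median too long in 6–22% of trials.
- 20–30% liable (about 3–6 patients): 0.27–1.11 months, and 23–60% of trials.
- Last-scan censoring leaves −0.01 to +0.05 months.

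When patients switch shortly before progression (5–30% liable), the planned rule overstates by 0.15–1.87 months and last-scan censoring by 0.06–1.41. Counting the switch as an event understates by 0.06–0.47.

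**PFS, large-sample check.** Assume exponential PFS with median 2.5 months (6-month PFS 2^(−6/2.5) = 19%), continuous scanning, median post-progression survival 7 months, and a data cut 12 months after last entry. If 10%, 20% or 30% stop scans before progression, last-contact censoring gives medians of 2.6, 2.8 and 3.1 months and 6-month PFS of 23%, 28% and 33%. Censoring when scans stop returns 2.5 months and 19% throughout.

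**DOR, formula.** Let λ = ln 2/m be the constant hazard of progression or death, and s the share of response endings that are deaths. Censoring deaths leaves hazard (1 − s)λ, so the median becomes m/(1 − s): +5% at s = 5%, +11% at 10%, +25% at 20%. With m = 6 months and s = 20%, it is 6/0.8 = 7.5 months.

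**DOR, small example.** Take five responses ending at 2, 3, 4, 6 and 9 months. With all counted as events, S falls 0.8, 0.6, 0.4, so the median is 4. If the month-3 ending is a death and is censored, S is 0.8 at month 2, 0.8 × 2/3 = 0.533 at month 4 and 0.533 × 1/2 = 0.267 at month 6, so the median is 6. Censoring each ending in turn gives 4, 6, 6, 4, 4, so 2 of 5 placements move the median. With two deaths, 7 of 10 placements move it (five to 6 months, two to 9).

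**The case against.** **The term is undefined.** The follow-up column in section 10.0 holds both scans and survival calls, so for PFS an analyst could take last follow-up to mean the last disease assessment. That reading is possible. But OS has the same sentence, where that reading would be wrong, and nothing directs the analyst to separate the two. If the last scan is meant, one sentence settles it.

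**Exposure is narrow.** Scans run every 2 cycles on treatment and every 3 months after stopping for other reasons. Section 12.4 asks for every effort to document progression after discontinuation, and death is a PFS event, which limits the excess time. This stands: only patients who switch therapy or miss scans before documented progression are affected.

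**The larger figures rest on assumed rates.** This also stands. At 5–10% liable with unrelated switching, the bias is about 2–9 days. The 6-week scan grid alone shifts the median by more, though equally under every rule. The simulation's reference also scans everyone every 6 weeks, whereas footnote 4 schedules 3-monthly scans off treatment.

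**Last-scan censoring is not a cure.** In the 20% rows with switching just before progression, it leaves 0.45 of 0.74 months (true median 2.5) and 0.80 of 1.14 (true median 4). This is correct and is the reason for the sensitivity analysis.

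**DOR is consistently defined as time to progression among responders.** It is, but it then treats a death differently from PFS in the same trial and reads longer for it. The five-responder example uses the minimum for success. At a 30% response rate the expected number is 0.30 × 25 = 7.5, where one death usually matters less.

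**Conclusion.** The concern holds. As written, the PFS and DOR rule allows censoring past the last scan, and DOR censors deaths. Both can only lengthen the reported medians when they apply. The direction follows from the text; the size does not, because the documents give no rate of early switching or of death in response. A plausible low-end PFS effect is a few days. It reaches about a month only if 20–30% are liable to switch or if switching anticipates progression. DOR is sensitive because responders may be few. The primary response-rate decision and the sample size are unaffected, so this should be corrected but does not threaten the main conclusion.

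**What to change.** - **Section 14.1, items 2 and 4:** censor patients without an event at the last adequate tumour assessment before any new anti-cancer therapy. Keep last follow-up for OS only.
- **Sections 2.2, 12.4 and 14.1:** end DOR at documented progression or death from any cause, matching PFS.
- **Sensitivity analysis:** add one that counts the start of new therapy as an event, because censoring there can be informative. It errs in the other direction: with unrelated switching, 10% liable and a true median of 4, it gives 4.22 against 4.77 months. It should be read beside the main result and should not replace it.

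The cost is a few sentences, one extra analysis and one date field. The start date of new anti-cancer therapy must be captured, and the data list in section 16.0 does not name it, although footnote 4 already makes that event a reason to stop scans. Visits, sample size and the 5/25 rule do not change. The reported PFS and DOR may be slightly shorter, and last-scan censoring can still overstate PFS if patients switch because they are worsening.

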## **15.0 RESEARCH PARTICIPANT REGISTRATION AND RANDOMIZATION PROCEDURES**

## **15.1 Research Participant Registration**

Confirm eligibility as defined in the section entitled Criteria for Patient/Subject Eligibility.

Obtain informed consent, by following procedures defined in section entitled Informed Consent Procedures.

During the registration process registering individuals will be required to complete a protocol specific Eligibility Checklist.

All participants must be registered through the Protocol Participant Registration (PPR) Office at Memorial Sloan-Kettering Cancer Center. PPR is available Monday through Friday from 8:30am – 5:30pm at [contact]. Registrations must be submitted via the PPR Electronic Registration System (<http://ppr/>). The completed signature page of the written consent/RA or verbal script/RA, a completed Eligibility Checklist and other relevant documents must be uploaded via the PPR Electronic Registration System.

## **15.2 Randomization**

NA

## **16.0 DATA MANAGEMENT ISSUES**

A research study assistant (RSA) will be assigned to study. The responsibilities of the RSA include project compliance, data collection, extraction and data entry, data reporting, coordination of the activities of the protocol study team and, and of the flow of regulatory paperwork.

The data collected for the study will be entered into a secure database (CRDB). All routine blood test results required per the protocol will be captured in CRDB in addition to baseline medical conditions and disease information, response assessments, off-study documentation, and toxicity grade and attribution. Source documentation will be available to support the computerized patient record.

MSKCC will hold the IND and will be responsible for all safety monitoring. All SAEs will be reported to the MSKCC IRB. The safety of the study will be monitored by the MSKCC Data and Safety Monitoring Committee.

Weekly registration reports will be generated by the RSA and reviewed by the PI to monitor patient accruals and completeness of registration data. Routine data quality reports will be generated to assess missing data and inconsistencies.

Accrual rates and extent and accuracy of evaluations and follow up will be monitored periodically throughout the study. Recurrent lapses in data collection, deviations or

violations will be discussed with the study team and a corrective plan will be generated. Accrual goals and factors impacting accrual goals will be discussed at the weekly New Patient/Protocol meetings.

### **16.1 Quality Assurance**

The data and safety monitoring plan at Memorial Sloan-Kettering Cancer Center was approved by the National Cancer Institute in September 2001. The plan addressed the new policies set forth by the NCI and the document entitled "Policy of the National Cancer Institute for data and safety monitoring of clinical trials" which can be found at <http://grants.nih.gov/grants/guide/notice-files/not98-084.html>. The DSM plans at MSKCC were established and are monitored by the Office of Clinical Research. The MSKCC data and safety monitoring plan can be found on the MSKCC Internet at [http://inside2/clinresearch/Documents/MSKCC Data and Safety Monitoring Plans.pdf](http://inside2/clinresearch/Documents/MSKCC%20Data%20and%20Safety%20Monitoring%20Plans.pdf).

There are several different mechanisms by which clinical trials are monitored for data, safety and quality. There are institutional processes in place for quality assurance (e.g., protocol monitoring, compliance and data verification audits, therapeutic response, and staff education on clinical research QA) and departmental procedures for quality control, plus there are two institutional committees that are responsible for monitoring the activities of our clinical trials programs. Memorial Sloan-Kettering Cancer Center has set up three distinct monitoring processes for our clinical trials program. There are two sub-committees that have the responsibility of data and safety monitoring. These are joint sub-committees with dual-reporting responsibilities. The Data and Safety Monitoring Committee (DSMC) is the sub-committee responsible for monitoring all Phase 1, 2, 1/2, pilot and non-phase clinical trials. The Data and Safety Monitoring Board (DSMB) is the sub-committee responsible for monitoring Phase 3 randomized clinical trials. The Therapeutic Response Review Committee (TRRC) is the sub-committee of Research Council responsible for the independent therapeutic response review for participants in IRB/PB approved clinical trials where therapeutic efficacy is a stated primary objective; typically phase 2 and 3 trials. Formal monitoring of such studies is designed to ensure that the interests of the participants are being scrutinized on a regular basis, and that the trial is progressing in a satisfactory manner.

The Data and Safety Monitoring Committee (DSMC) convenes once per quarter and monitors the risk participants are exposed to, the progress of the study, the adequacy of the data storage and whether sufficient data are being entered into the CRDB. The DSMC monitors phase 1, 2, 1/2, pilot and non-phase trials that are not being monitored by an industrial sponsor, and which meet the NCI definition of a Clinical Trial. This trial will qualify for monitoring by the DSMC.

During the protocol development and review process, each protocol will be assessed for its level of risk and degree of monitoring required, and the monitoring procedures will be

established at the time of protocol activation. A detailed description of the data to be collected, process of data collection (i.e., data manager and/or data management office), database that will be utilized for data collection and storage (e.g., Clinical Research Database (CRDB), user-supported software), reporting requirements of the data to the institution (IRB), the sponsor and/or governing agency.

